## 10.6 Radiographic Assessments and Definition of Radiographic Treatment Response

Staging imaging will be performed according to the study calendar in [section 5.0](#) at baseline, one month post SBRT (clinical exam), 7 weeks (+/-1wk) post SBRT (clinical exam, triphasic CT for purpose of evaluating resectability) and 12 weeks (+/-5days) post SBRT (clinical exam, CT and endoscopy), in addition to regular q3 month follow up visits. Progression of disease will be evaluated at each time point. Radiographic response will be measured according to a modified Response Evaluation Criteria in Solid Tumors (RECIST) as described in [section 10.6.3](#) and [10.6.4](#) below. Only response assessment of the primary target will be considered for biostatistical purposes of the primary analysis, since these targets are affected by radiation. Overall Response will be considered per RECIST 1.1 for PFS calculations (secondary endpoint), but not used for the primary endpoint of determining the MTD. All imaging will be interpreted by an MDACC-affiliated radiologist. All participating sites will submit scans to MDACC for review per the Study Manual. The same method of cross-sectional imaging used at baseline must be used at each follow up evaluation for treatment response.

### 10.6.1 Measurable Lesion

The measurable lesion must measure  $\geq 1$ cm in the longest dimension utilizing CT scan thickness  $< 5$  mm.

### 10.6.2 Non-measurable Lesions

Non-measurable disease will include all lesions  $< 10$ cm in longest dimension, in addition to truly non-measurable disease including leptomeningeal disease, ascites, pleural or pericardial effusion, inflammatory breast disease, lymphangitic involvement of skin or lung, abdominal mass/organomegaly that cannot be confirmed on imaging.

### 10.6.3 Target Lesion

The target lesion will be the primary pancreatic tumor classified as measurable disease. The response within the target lesion will be used for statistical consideration. Non-target lesions will also be tracked and measured, but will be considered only for the purpose of determining progression-free survival. The primary target lesion will be considered in evaluating local control.

### 10.6.4 Response Criteria Definitions

**Complete Response (CR):** Disappearance of the target lesion. Any pathologic lymph nodes (target or non-target) must have reduction in short axis to  $< 10$ mm

**Partial Response (PR):** At least a 30% decrease in the diameter of the target lesions, utilizing baseline measurements as reference.

**Stable Disease (SD):** Neither sufficient shrinkage to qualify for PR nor sufficient increase to qualify for Local Progressive Disease (LPD).

**Local Progressive Disease (LPD):** At least a 20% increase in the the longest diameter of the target lesion, utilizing baseline measurement (scan) as reference. The measurement must also demonstrate an absolute increase of at least 5mm. If the study in which LPD is noted at the 6-8 week post-SBRT scan, LPD must be confirmed in the subsequent scan (at the 12 week post SBRT

scan) to rule out post-radiation inflammation from SBRT. If a repeat scan is indeterminate, additional imaging modalities including MRI or PET/CT can be utilized. Progression will be retroactively dated to the initial scan on which the LPD was suspected.

**Distant Progressive Disease (DPD):** The appearance of new unequivocal metastatic lesions on follow up imaging will denote distant progression. The finding of a new lesion must not be attributable to differences in imaging technique, change of imaging modality, or findings thought to represent something other than tumor, especially if primary target lesions shows partial or complete response. If a new lesion is equivocal but suspicious for DPD, continued follow up should be done until it becomes unequivocal. Progression will be retroactively dated to the initial scan on which the DPD was suspected.

**Biochemical Response (BR):** Elevated CA19-9 level will not be used to determine disease progression, but will be used to measure biochemical progression free survival (bPFS). A CA 19-9 level that decreases by 50% from pre-treatment value will be considered a biochemical response.

**Biochemical Failure (BF):** If the CA 19-9 level increases by 50% on 2 successive measures from the lowest recorded on study value, it will be considered biochemical failure.

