| Pancreatic Protocol CT(3,6) (for resectability assessment)                                 |       |       |       |       | X     |       |       |
| MRI abdomen w/ and w/o contrast (for assessment of small bowel toxicity), is possible.     | X (3) |       |       |       |       | X (3) |       |
| Restaging CT Scan of Chest/Abd/Pelvis  | X (3) |       |       |       |       | X (3) | X(3)  |
| Randomization****  |       | X     |       |       |       |       |       |

\* Endoscopy for fiducial placement and biopsies may occur anytime between screening and radiation simulation

\*\* After the 12 week visit, patients will continue in follow-up with physical examinations, labs, and staging scans every 3 months (+/- 28 days) post-SBRT until they have reached 36 months post-SBRT or until local progression. Thereafter, clinical status information is required every 6 months for 5 years post-SBRT, to include survival information and toxicity data. This information may be obtained via telephone call if patient is lost to clinic follow up. For patients who discontinue treatment for progressive disease or are removed from protocol treatment, survival information is required every 6 months for 5 years post-SBRT. Adverse events including radiation toxicity up to 1 year post-SBRT will be assessed during visits and phone calls, and recorded in the case report form (See section 9.3 for details).

\*\*\* Simulation should be within 30 days of SBRT. If simulation is done > 2 weeks prior to treatment start, a verification simulation should be performed in the week prior to treatment start.

\*\*\*\* Randomization will occur following completion of the radiation simulation. See Study Manual for details on the registration and randomization process.

1 Medical and Disease History, including pathology, collected within the Screening and Baseline Period will include information deemed medically-relevant by the Investigator (or designee). May be performed by physician, NP, or PA responsible for oncologic care of the patient. Vitals may be collected by RN or MA.

2 To be completed ONCE prior to treatment. The study files will contain examples and IRB approval of the assessments.

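### Local progression is judged only against the baseline diameter, with no rule for reappearance after complete response or resection, so local failure in follow-up can be missed or dated late

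*Combined protocol and SAP*

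**What the plan says.** Section 10.6.4 sets the response categories for the primary tumour.

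- Complete response: "Disappearance of the target lesion", with a short-axis condition for pathologic nodes.
- Partial response: "At least a 30% decrease in the diameter of the target lesions, utilizing baseline measurements as reference".
- LPD: at least a 20% increase in the "longest diameter of the target lesion, utilizing baseline measurement (scan) as reference". It adds: "The measurement must also demonstrate an absolute increase of at least 5mm". No separate reference is given for the 5 mm, so I read it as baseline too.
- Stable disease: whatever is neither partial response nor LPD.
- Distant progression: new unequivocal metastatic lesions.

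The section has no rule for tumour reappearing at the primary site after complete response or resection. For biochemical failure it uses a different kind of reference: "If the CA 19-9 level increases by 50% on 2 successive measures from the lowest recorded on study value".

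Three other places set the reach of the definition. Section 10.6.3 states: "The primary target lesion will be considered in evaluating local control". The double-asterisk footnote to the Section 5.0 calendar has patients scanned every 3 months "until they have reached 36 months post-SBRT or until local progression". Section 10.6 sends PFS to RECIST 1.1 and keeps the modified criteria, applied to the primary target, for the primary analysis.

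**The concern.** A baseline reference suits a single early reading such as the day-90 Efficacy score. Over three years of scans it behaves differently. Once a tumour has shrunk, it must regain all the lost diameter and then grow a further 20% before the plan calls local progression. Until then it is partial response or stable disease, even if it has doubled from its smallest size.

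The effect grows with depth of response. Sections 1.2.7 and 1.2.8 hypothesise that GC4419 enhances anti-tumour effect, and Section 2.1 expects better local control from higher doses. If an arm or dose level produces more shrinkage, it gains apparent local-control time from the definition, whether or not the control is durable. Section 1.2.3 treats local progression as important in this population, so local-control figures are likely to be read with interest if reported.

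**Working it through.** **Inputs.** The 20% and 5 mm thresholds, the baseline reference and the 30% partial-response limit come from Section 10.6.4. The documents give no tumour sizes, response rates or regrowth rates. Baselines of 20-50 mm, shrinkage of 10-100% and a diameter doubling time of 6-12 months on regrowth are therefore assumptions. The plan states no figure on this point to reproduce.

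**Step 1: classification.** Let b be the baseline diameter, n the smallest on-study diameter and x the current diameter. The plan calls LPD when x reaches max(1.2b, b + 5). For 40 mm shrinking to 20 mm and returning to 40 mm:

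- partial response up to 0.7 × 40 = 28 mm
- stable disease above 28 mm, including at 40 mm (0% change from baseline)
- LPD only from max(48, 45) = 48 mm

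With the smallest diameter as reference, LPD would start at max(1.2 × 20, 20 + 5) = 25 mm.

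Under the plan, regrowth to the original size is stable disease at every baseline and depth of response, complete response included. With the smallest-diameter reference it is LPD for every shrinkage of 30% or more at baselines of 20-50 mm, and for 20% shrinkage at baselines of 25 mm or more. It is not LPD after 10% shrinkage under either rule.

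**Step 2: direction.** Because n ≤ b, any x with x ≥ 1.2b and x − b ≥ 5 also satisfies x ≥ 1.2n and x − n ≥ 5. Every LPD under the plan is thus LPD under the smallest-diameter rule, at the same scan or earlier. The baseline rule can only miss or delay local failure.

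**Step 3: growth needed from the smallest diameter.** For b ≥ 25 mm the 20% condition governs, and the ratio is 1.2b/n:

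- 30% reduction: 1.2/0.7 = 1.71, or 71% growth
- 50% reduction: 1.2/0.5 = 2.40, or 140% growth

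For b = 20 mm the 5 mm condition governs (threshold 25 mm): 25/14 = 1.79 (79%) and 25/10 = 2.50 (150%).

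**Step 4: delay.** Delay = log2(plan threshold / smallest-diameter threshold) × doubling time, with the 5 mm condition in both thresholds.

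| Baseline | Reduction | Thresholds (mm) | log2 of ratio | Delay at 6-12 months doubling |
|---|---|---|---|---|
| 20 mm | 50% | 25 vs 15 | 0.74 | 4.4-8.8 months |
| 40 mm | 50% | 48 vs 25 | 0.94 | 5.6-11.3 months |
| 50 mm or more | 50% | 60 vs 30 (at 50 mm) | 1.00 | 6-12 months |
| 20 mm | 30% | 25 vs 19 | 0.40 | 2.4-4.8 months |
| about 36 mm or more | 30% | ratio 1/0.7 | 0.51 | 3.1-6.2 months |

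The limits of 50 mm and about 36 mm are where n reaches 25 mm (25/0.5 = 50; 25/0.7 = 35.7), so that 20% of n is at least 5 mm. On a 3-monthly schedule, 2.4 to 12 months is about one to four scan intervals.

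**Step 5: reappearance.** After complete response or resection, recurrent tumour is LPD only from max(1.2b, b + 5). A 30 mm recurrence is not LPD if the baseline exceeded 25 mm, but it is LPD for a baseline of 25 mm or less. A 15 mm recurrence in the bed is not LPD for any baseline above 10 mm. The distant-progression rule does not catch it, since that rule requires metastatic lesions.

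**The case against.** The strongest reply is that no planned result depends on this. Local control is absent from the primary, secondary and exploratory objectives (Sections 2.2 to 2.4) and from the analyses in Section 12.9.2. Section 10.6.3 names it in one sentence, with no time origin, horizon, estimator or arm comparison. The calendar footnote is a scanning rule and does not cite the LPD definition. Section 12.9.1 defers analysis detail to a formal SAP. All of this stands and keeps the severity modest. It does not remove the point: local control is to be evaluated on this lesion, the only local-progression definition supplied is the one in Section 10.6.4, and the supplied text contains no rule based on the smallest diameter or on recurrence.

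Three stronger readings should be resisted.

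- **A reader might infer that dose selection is biased.** Section 12.1 makes Efficacy a comparison with baseline at day 90. The only earlier scheduled scan is the 7-week CT, done on clinical necessity, so a tumour would have to shrink and regrow between weeks 7 and 12 for the reference to matter.
- **A reader might infer that PFS is inflated.** Section 10.6 assigns PFS to RECIST 1.1, so the LPD definition does not govern it.
- **A reader might infer from the pooled 1-year survival of 51.6% in Section 1.2.4 that many patients would die with local failure unrecorded.** That figure pools external studies and says nothing about responders whose tumours regrow here.

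The CA 19-9 contrast is also weak as evidence of error. It concerns a separate marker that is expressly not used for disease progression, and it shows only that a lowest-value reference was available to the authors. Finally, the diameters are being measured anyway, so a sensitivity analysis with the smallest-diameter reference stays possible.

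**Conclusion.** The point holds for local control and local progression in follow-up. The classification and the direction of bias follow from the definitions alone. The growth figures of 71% and 140% need only a baseline of 25 mm or more. The delays of about 2.4 to 12 months rest on an assumed doubling time and on the illustrative sizes and depths of response. The bias in the trial's local-control figures cannot be computed, because the documents give no response or regrowth rates. Any difference in bias between arms or dose levels is conditional on a difference in shrinkage and on a comparison of local control that the documents do not specify. This is a worthwhile, inexpensive correction to a definition and does not threaten the primary or secondary endpoints.

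**What to change.** In Section 10.6.4, keep the baseline reference for the day-90 Efficacy score. For local control and local progression in follow-up, define LPD as an increase of at least 20% and at least 5 mm over the smallest on-study diameter, baseline included. Count reappearance of tumour at the primary site after complete response or resection as local failure.

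The cost is a short text change. It uses scans already scheduled and diameters already measured, with no added visits, imaging or patients. The downside is that reported local-control figures become somewhat less favourable.

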## 10.7 Surgical and Pathologic Determination of Treatment Response

### 10.7.1 Evaluation of Resectability

Determination of locally advanced disease/ technically unresectable disease will be determined at diagnosis and at 6 to 8 weeks post treatment by surgical collaborators in the multidisciplinary setting. This will be generally according to the following criteria at the surgeon's discretion:

- Greater than 180 degree tumor involvement of the superior mesenteric artery
- Greater than 180 degree tumor involvement of the celiac axis, including major branches of the celiac axis that render it unresectable (e.g. common hepatic artery).
- Tumor involvement of the first branch of the SMA that is not surgically reconstructible
- Long segment involvement of the superior mesenteric vein/portal vein or hepatic artery that is not surgically reconstructible

### 10.7.2 Histologic Response

Should the patient undergo surgical resection, pathologic review will be performed locally to determine histologic response according to the following criteria:

- **Pathologic Complete Response (pCR):** 0% residual tumor cells in specimen
- **Near Pathologic Complete Response (pNR):** 1 to < 5% residual tumor cells in the specimen
- **Partial Pathologic Response (pPR):** ≥ 5% to 30% residual tumor cells in the specimen

### 10.7.3 Margin Status at Resection

Margins will be assessed according to location (common bile duct, SMA or pancreatic neck) according to the following criteria:

- **R0:** Macroscopically complete tumor removal with negative microscopic surgical margins.
- **R1:** Macroscopically complete tumor removal with positive microscopic margins (any or all).
- **R2:** Macroscopically incomplete tumor removal with known or suspected residual gross disease.

## 10.8 Patient Reported Outcomes using PRO-CTCAE and LASA

The PRO-CTCAE and LASA items will be used to determine QOL and patient reported disease and treatment related symptoms.

We do not anticipate major differences in physical function between the two arms and various dose levels; however, the various domains of the PRO-CTCAE will help elucidate differences in short term effects of SBRT and GC4419 on patients' well-being. Higher doses of radiation may be more effective in alleviating patients' abdominal pain, nausea and obstructive symptoms.

The IRB-approved questionnaires within the protocol can be provided to patients for completion. Please include patient identifiers on all pages. At visits in which the questionnaires are to be completed, the questionnaires should be given to the patient before any discussion of the patient's health status or test results.

The single item linear self-assessment or LASA items for overall QOL, fatigue, mental, and physical quality of life will be used to assess the quality of life of patients randomized to each treatment arm. These single items have been demonstrated to be prognostic for survival in general cancer populations and in pancreatic cancers. These LASA items will be assessed at screening/baseline and at specified follow up visits. Overall QOL, fatigue, mental and physical quality of life will be assessed at post treatment follow-up.

Potential treatment-related symptomatic adverse events will be measured using the Patient-Reported Outcomes version of the CTCAE (PRO-CTCAE). To improve precision and patient-centeredness in the capture of symptomatic AEs, NCI funded a team of investigators led by [name] to develop a library of patient-reported outcome (PRO) items to supplement the CTCAE, called the PRO-CTCAE. Of the 790 AEs in the CTCAE, 78 were identified as amenable to patient self-report. For each of these AEs, PRO items were created reflecting the attributes of frequency (with response options of "never", "rarely", "occasionally", "frequently", or "almost constantly"), severity ("none", "mild", "moderate", "severe", or "very severe"), interference with usual or daily activities ("not at all", "a little bit", "somewhat", "quite a bit", or "very much"), amount ("not at all", "a little bit", "somewhat", "quite a bit", or "very much"), or presence ("no" or "yes"). One to three attributes were selected for any given AE depending on the content of the CTCAE criteria for that AE and the nature of that particular AE. In total, 124 individual items represent the 78 symptomatic AEs currently in the PRO-CTCAE item library. Each item includes a plain language term for the AE, the attribute of interest, and the standard recall period of "the past 7 days." Cognitive interviews previously determined a high level of patient understanding and meaningfulness of the items and a national multi-site validation study showed that items were valid, reliable, and sensitive to change. For this study, the following symptomatic AEs selected were based on the known symptomatic toxicities occurring in >10% of patients treated with SBRT. Specifically, at the selected time points, patients will complete 15 PRO-CTCAE items measuring: Fatigue, nausea, vomiting, diarrhea,

neuropathy, abdominal discomfort, abdominal bloating, pain, heartburn, decreased appetite, dry mouth, taste changes, itching (pruritis), depression, anxiety. The recall period will be 2 weeks. AEs will be measured at baseline, end of SBRT and at follow up visits. Reporting will occur using table based technology or paper booklets, as available.

The final survey contains only 4 LASA items plus 15 PRO-CTCAE items it is anticipated that the questionnaire will take approximately 10 minutes for the patient to complete at each administration time point. We anticipate having questionnaires available in English and Spanish. Patients may decline to complete a questionnaire at any time. The primary reason for each missed questionnaire will be collected on a case report form.

## **11.0 END OF TREATMENT/INTERVENTION**

### **11.1 Duration of Treatment**

The treatment period will begin the first day of SBRT and GC4419/placebo treatment and end the final day of SBRT and GC4419/placebo treatment.

Patients may *not* receive additional anti-cancer therapy during the 90 day follow up period, except in the instance of progression of disease. After 90 days, patients may receive therapy at the treating physician's discretion. Any anti-cancer therapy should be recorded in the case report form.

### **11.2 Managing ineligible patients and registered patients who never receive protocol intervention**

Patients who are randomized but later deemed ineligible for SBRT or voluntarily withdraw from the study will still be eligible for follow up imaging and correlative studies, in addition to PRO data, should they so choose. These patients will not be considered in the n=48 patients to be randomized, and will not be considered in the final analyses for primary and secondary endpoints. The reason for not receiving protocol intervention must be documented.

### **11.3 Extraordinary Medical Circumstances**

If, at any time the constraints of this protocol are detrimental to the patient's health and/or the patient no longer wishes to continue protocol therapy, protocol therapy shall be discontinued. In this event:

- Document the reason(s) for discontinuation of therapy on the case report forms.
- Follow the patient for protocol endpoints as required by the Study Calendar.

## 12.0 STATISTICAL CONSIDERATIONS

### 12.1 Study Primary Endpoint

For the purposes of dose finding the following definitions will be used in determining MTD:

- **Toxicity:** CTCAE grade 3 or 4 related gastro-intestinal (GI) toxicity or death, occurring within 90 days from the start of therapy.
- **Efficacy:** Radiographic stable disease (SD) or better based on modified RECIST criteria, ([section 10.6.4](#)), compared to baseline imaging of the same type, as evaluated at day 90 from the start of therapy.
  - If a patient dies or has local progressive disease (LPD) at some time  $t^*$  prior to day 90, then Efficacy will be scored at the time  $t^*$  as not occurring for that patient.
  - If a patient undergoes resection at some time  $t^*$  prior to day 90, then Efficacy will be scored as occurring at  $t^*$  and Toxicity will be scored as not occurring within 90 days for that patient.

Prior to determination of final MTD, 12 month toxicity will also be evaluated. If any dose level demonstrates >20% grade 4 or 5 gastrointestinal toxicity related to radiation, the preceding dose level will be used as the final MTD.

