**Assessment Criteria:**

Toxicity:

- Unacceptable toxicity of SBRT will be defined as related, CTCAE grade 3 or 4 gastrointestinal (GI) toxicity or death, occurring within 90 days from the start of therapy.

Efficacy:

- Radiographic stable disease (SD) or better based on modified RECIST criteria for the primary target, compared to baseline imaging of the same type, as evaluated at day 90 from the start of therapy.

Safety:

National Cancer Institute - Common Terminology Criteria for Adverse Events, version 4.03 up to 1 year post-SBRT Patient-Reported Outcomes:

- Linear Analogue Self Assessment (LASA)
- NCI Patient Reported Outcomes CTCAE (PRO-CTCAE) version 1.0

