## 12.4 Phase I-II Dose Finding Design

Dose-finding will be done using the sequentially adaptive phase I-II Late onset Efficacy-Toxicity (LO-ET) trade-off-based design. For the purpose of dose-finding, as stated in [section 12.1](#):

- **Toxicity** is defined as a grade 3 or 4 gastro-intestinal (GI) toxicity, or death, occurring within 90 days from the start of therapy. For the purpose of dose-finding
- **Efficacy** is defined as stable disease (SD) or better, compared to baseline, as evaluated at day 90 from the start of therapy ([section 10.6.4](#)).

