## 12.9 Implementation

### 12.9.1 LO-ET Trial Implementation

The Late-Onset Efficacy-Toxicity (LO-ET) design will be implemented using the specialized computer program developed by Jin et al. During trial conduct, application of the statistical design will be carried by [name], a Statistical Analyst in the Department of Biostatistics. This will include (1) randomization of each patient at entry between the two arms, RT+ GC4419 versus RT only, and (2) adaptive dose assignment within each arm using the LO-ET method. Outcome-adaptive dose-finding will be done by inputting the current trial data and running the specialized computer program that implements the LO-ET method. This process will require close interaction between [name] and personnel in the clinic, including repeatedly providing [name] with all dose-outcome data from all previously enrolled patients, including each previous patient's time of Toxicity occurrence or current follow up time without Toxicity, up to the defined 90-day observation interval, and whether efficacy occurred at day 90. Critical variable data (provided within your Study Manual) should be entered into the electronic data capture clinical database in a timely fashion to ensure data is included in the ongoing analysis for SBRT dose level assignments. [name], a Senior Statistical in the Department of Biostatistics, will serve as a backup for [name] in the process of trial conduct. Additional statistical support or input will be provided as required by Drs. [name] and [name]. Details and procedures related to the various safety, efficacy, and correlative analyses will be provided in a formal Statistical Analysis Plan.

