### 12.9.2 Secondary Endpoints and Analysis

Secondary outcomes will include progression-free survival (PFS) time and overall response rate in addition to rate of long-term toxicity, surgical resection and rates of R0 and pathologic complete response at resection. Unadjusted distributions of the time-to-event outcomes PFS and OS will be estimated using the method of Kaplan and Meier and their relationship to prognostic covariates and RT cell dose level will be evaluated by Bayesian piecewise exponential survival regression.

Resectability will be assessed at the seven week time point. If a patient goes on to resection, he or she will be categorized as acceptable efficacy. If the patient is deemed unresectable, efficacy will be reassessed at 12 weeks. Toxicity will also be assessed at the 12 week timepoint and descriptive statistics will be generated. If endoscopy exhibits severe toxicity, the patient will be deemed as unacceptable toxicity.

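### As worded, the resection rule in 12.1 cancels a related grade 3-4 GI toxicity already seen before surgery, and it conflicts with the Toxicity definition when a resected patient dies before day 90

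*Combined protocol and SAP*

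**What the plan says.** Section 12.1 defines Toxicity for dose finding as a related grade 3 or 4 GI event, or death, in the first 90 days. Efficacy is stable disease or better at day 90. Two sub-rules follow.

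- Death or local progression: "If a patient dies or has local progressive disease (LPD) at some time" t* before day 90, Efficacy is scored at t* as not occurring.
- Resection at t* before day 90: Efficacy is scored as occurring at t*, "and Toxicity will be scored as not occurring within 90 days for that patient".

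Section 12.1 also has a 12-month check: "If any dose level demonstrates >20% grade 4 or 5 gastrointestinal toxicity related to radiation", the preceding level becomes the final MTD.

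Other sections touch the same ground without the no-Toxicity clause:

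- The synopsis (Assessment Criteria) gives unacceptable toxicity as related grade 3 or 4 "gastrointestinal (GI) toxicity or death, occurring within 90 days from the start of therapy".
- Section 12.4 refers back to 12.1 and restates Toxicity as "grade 3 or 4 gastro-intestinal (GI) toxicity, or death, occurring within 90 days from the start of therapy".
- Section 12.9.2 restates the resection rule for Efficacy only: "If a patient goes on to resection, he or she will be categorized as acceptable efficacy".
- Section 12.9.1 has the analyst receive each patient's "time of Toxicity occurrence or current follow up time without Toxicity", and does not mention resection.

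**The concern.** The resection rule ties Efficacy to t* but ties Toxicity to the full 90 days. Nothing limits it to events after t* or to patients event-free at t*. Followed as written, a patient with a related grade 3 GI bleed in week 3 who is resected in week 9 enters the model as Efficacy yes, Toxicity no. Under that reading the error runs one way: scored Toxicity can fall but never rise.

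Timing makes pre-surgery events a real part of what could be lost. Section 10.7.1 places the resectability review "at 6 to 8 weeks post treatment by surgical collaborators", and the study calendar puts the seven-week visit at day 54, so more than half the window has usually passed before surgery. Scored Toxicity feeds dose assignment within each arm, the acceptability rule in 12.6 (limit 0.15, cut-off 0.10) and MTD selection, which is the primary objective.

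A second gap needs no literal reading. A patient resected and then dead before day 90 has Toxicity by definition and no Toxicity by the resection rule.

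**Working it through.** **Reading the rules against each other**

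| Patient, all before day 90 | Definition and death/LPD rule | Resection rule, literal | Resection rule, milder reading |
|---|---|---|---|
| GI event, then resection | Toxicity yes | Toxicity no | Toxicity yes |
| Resection, then death | Efficacy no, Toxicity yes | Efficacy yes, Toxicity no | Efficacy yes, Toxicity no |

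The plan gives no figure to reproduce here. The arithmetic below is for scale only.

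**Inputs from the documents**
- 24 patients per arm (12.3).
- Acceptability limit 0.15 and cut-off 0.10 (12.6).
- Prior mean toxicity 0.02 at level 1 and prior effective sample size 1 (12.7).
- Half of events fall in the later half of the evaluation interval (12.8). With an even spread within each half, the share of events by day d is F = d/90, so F = 54/90 = 0.60 at day 54.

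**Assumptions, not in the documents**
- True toxicity rate pT = 0.20 in all 24 patients.
- Surgery at day 54.
- Share resected before day 90, r = 10% to 40%.
- Resection either independent of toxicity (r_tox = r), or half as likely after toxicity: r_tox = 0.5r/(1 − pT + 0.5pT) = 0.5r/0.90.

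**Events lost.** The comparison is between the literal rule and one that keeps events before t* but, like the literal rule, scores none after it.
- Literal: scored rate = pT(1 − r_tox).
- Keeping earlier events: scored rate = pT(1 − r_tox(1 − F)).
- Difference = pT × r_tox × F. For r = 10%, independent: 0.20 × 0.10 × 0.60 = 0.012, and × 24 = 0.29 events.

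**Can one event matter?** As a stand-in for the LO-ET toxicity rule at level 1, with all patients fully followed, take the posterior Beta(0.02 + x, 0.98 + n − x) and call the dose unacceptable when Pr(pT < 0.15) < 0.10.
- n = 3: 1 event gives 0.375; 2 events give 0.058.
- n = 6: 2 events give 0.218; 3 events give 0.046.
- n = 9: 3 events give 0.137; 4 events give 0.033.

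So the bound k is 2 of 3, 3 of 6 or 4 of 9, and one dropped event can move a level across it.

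**How often would it?** Per patient, let a = pT × r_tox × F (event lost), b = pT(1 − r_tox) (event counted either way) and c = 1 − a − b. The decision changes when lost plus counted events reach k but counted events alone do not. For n = 3, k = 2, r = 10%, independent: a = 0.012, b = 0.18, c = 0.808, and 6abc + 3a²c + 3a²b + a³ = 0.01047 + 0.00035 + 0.00008 + 0.00000 = 0.0109.

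| r | 10% | 20% | 30% | 40% |
|---|---|---|---|---|
| Independent: events lost per arm | 0.29 | 0.58 | 0.86 | 1.15 |
| Independent: decision changes, n = 3 | 1.09% | 2.05% | 2.87% | 3.54% |
| Independent: decision changes, n = 6 | 1.34% | 2.42% | 3.22% | 3.75% |
| Half as likely: events lost per arm | 0.16 | 0.32 | 0.48 | 0.64 |
| Half as likely: decision changes, n = 3 | 0.62% | 1.20% | 1.75% | 2.24% |
| Half as likely: decision changes, n = 6 | 0.78% | 1.48% | 2.09% | 2.62% |

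**Sensitivity, independent case**
- pT = 0.10: 24 × 0.10 × 0.60 × r = 0.14 to 0.58 events; decision changes about 0.2% to 1.0%.
- pT = 0.20, surgery at day 75 (F = 75/90 = 0.833): 0.40 to 1.60 events; decision changes about 1.5% to 5.7%.
- If toxicity always precludes surgery, r_tox = 0 and nothing is lost.

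**The case against.** The best defence is that the literal reading is not the natural one. Both sub-rules sit under Efficacy and describe an event at t* that settles an outcome still open. Under 12.9.1 a toxicity before t* would normally already be in the data and already used for dosing, and nothing says an entered event is deleted when surgery follows. The rule may simply close out event-free patients, perhaps to keep post-operative events out of SBRT dose finding. This reading is plausible. It is not written, however, and the full 90-day wording points away from it. Section 12.9.1 defers analysis details to a formal Statistical Analysis Plan and data items to a Study Manual. Those texts are not in the document reviewed and might settle the point.

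On Efficacy, each sub-rule scores at its own t*, which suggests the first event decides. That narrows the ordering problem mainly to Toxicity after resection followed by death.

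The scale is also open to challenge. No Table 6 scenario uses 0.20, patients will be spread over three levels, day 54 is the resectability visit rather than a likely surgery date, and LO-ET models the levels jointly. Opportunity is limited too: criteria 2a to 2c enrol patients who are unresectable, not surgical candidates or refusing surgery, so early resection would come mainly from borderline cases (2d) or conversion.

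A reader might infer three stronger points, none of which the documents support.
- That observed toxicities are in fact being deleted. Nothing shows how any patient was scored.
- That the synopsis and 12.4 contradict 12.1 by omitting the clause. Section 12.4 points back to 12.1, and a synopsis is a summary.
- That a true rate of 0.30 would be scored as 0.15. That comes from 0.30 × (1 − 0.50): it needs half the patients resected and also removes events after t*, which are a separate question.

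**Conclusion.** The concern holds as a defect of wording in the primary-endpoint scoring. As written, the rule drops a related grade 3-4 GI event seen before resection, and no section of the document supplies an exception. The definition and the rule also give opposite Toxicity scores for a patient resected and then dead before day 90.

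The direction is known only under the literal reading. The size is not known, because the documents give neither an early-resection rate nor its association with toxicity. Under the stated assumptions it is about 0.2 to 1.2 events per arm, with a 0.6% to 4% chance at a given look of changing the level 1 toxicity decision: less at a lower toxicity rate, more with later surgery. No wrong MTD is shown.

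The 12-month check is a partial safeguard. It is not written in terms of scored Toxicity, so grade 4-5 radiation-related GI events in resected patients can still lower the final MTD. It omits grade 3 and comes after doses have been assigned. The point should be fixed because the same patient can be entered in two ways and the correction is cheap.

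**What to change.** Reword the resection rule in 12.1 along these lines:

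> If a patient undergoes resection at t* before day 90, Efficacy is scored as occurring at t*, unless LPD occurred earlier. A Toxicity that occurred before t* is retained.

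This makes explicit that the first event decides Efficacy; death cannot precede surgery, so only LPD needs naming. Do not add a sentence that scores every patient event-free at t* as having no Toxicity, since that would settle the open question by default.

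The sponsor should then reconcile the rule with the inclusion of death in the Toxicity definition and state in 12.1 how events after t*, including death, are scored. It is a trade-off: counting all later events may attribute operative deaths to SBRT, and counting none may miss late SBRT toxicity. Whatever is chosen, list those events separately. Because the sponsor is unblinded and interim efficacy results on the first 19 subjects go to investigators (12.9.3), make the choice without reference to arm-level results and record that in the amendment.

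Align the synopsis, 12.4 and 12.9.2. Re-score a resected patient only if an earlier Toxicity was entered as none, and do so before further dose assignments and final MTD selection.

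The cost is a short amendment with IRB review (14.1). Adverse events are already recorded to one year (9.3), so no new visits are needed. Scored toxicity may come out slightly higher. If no resected patient had an earlier event, the retention clause changes no score.
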